7.10.5 Unexpected adverse events

Any AE assessed at least as possibly related to the IP will be assessed for expectedness by the sponsor or designee. An AE is considered "unexpected" if its nature or severity is not consistent with information in the MC2-01 Investigator's Brochure(23) (for MC2-01 cream) or Daivobet[®] / Dovobet[®]Gel Summary of Product Characteristics (SmPC)(24) (for active comparator).

"Unexpected" as used in this definition, also refers to AEs that are mentioned in the Investigator's Brochure or SmPC as occurring with a class of drugs or as anticipated from the pharmacological properties of the drug but are not specifically mentioned as occurring with the particular drug under investigation.

7.10.6 Trial medication overdose

An overdose of the IP, i.e., a dose that is higher than the highest dose under clinical investigation or the known therapeutic dose, will be fully documented even if no toxic effects were observed and will be considered an AE.

The application should only be done once daily, and the treated area should not be >30% of the body surface area.

Use of MC2-01 cream in excessive amounts may cause elevated serum calcium, which should rapidly subside when treatment is discontinued. Excessive prolonged use of topical corticosteroids may suppress the pituitary-adrenal functions, resulting in secondary adrenal insufficiency that is usually reversible. In such cases, symptomatic treatment is indicated.

7.10.7 Pregnancy

Any pregnancy occurring from date of the Informed Consent signature until trial completion must be reported immediately to MC2 or designee as soon as it becomes known to the investigator and not later than within 24 hours of his/her knowledge of the occurrence of the pregnancy (see Section 7.10.9).

All pregnancies should be actively followed through to resolution (i.e., delivery, miscarriage, or abortion). The corresponding report(s) should be submitted within the same timelines as mentioned above. A pregnancy per se is not considered an SAE.

7.10.8 Serious adverse event

An SAE is any untoward medical occurrence that at any dose:

MC2 Therapeutics

- Results in death
- Is life-threatening
- Requires in-patient hospitalisation or prolongation of existing hospitalisation
- Results in persistent or significant disability/incapacity
- Is a congenital anomaly/birth defect, or is an important medical event
- Other serious or important medical event

The death of a subject enrolled in a trial is per se not an event, but an outcome. Any event resulting in a fatal outcome must be fully documented and reported, regardless of the causality relationship to the IP.

Any medical important events that may not result in death, be life-threatening, or require hospitalisation may be considered an SAE when, based on appropriate medical judgment, they may jeopardise the subject or the subject may require medical or surgical intervention to prevent one of the outcomes listed in the above definitions.

Any pre-planned hospitalisations that are known at the time of signing the informed consent form (ICF) will not be recorded as SAEs, however they will be recorded as AEs only.

Any SAE, whether or not deemed drug-related or expected, must be reported immediately to the MC2 or designee as soon as it becomes known to the investigator and not later than within 24 hours of his/her knowledge of the occurrence of an SAE (see Section 7.10.9). The investigator will document such events in the best possible detail on the SAE Report Form.

If the investigator becomes aware of an SAE after the end of the clinical trial that is possibly related to the IP, he/she must inform the sponsor immediately.

A SUSAR is an SAE that is both unexpected (not consistent with the current Investigator's Brochure(23) or Daivobet[®] / Dovobet[®] Gel SmPC(24) (for active comparator), and for which there is evidence to suggest a causal relationship between the drug and the SAE. The Institutional Review Board (IRB)/Independent Ethics Committee (IEC) will be informed of SUSARS according to local requirements. All investigators participating in the trial will also be notified of unexpected SAEs. The sponsor will report SAEs and other events requiring expedited reporting to regulatory authorities as required.

Investigator instructions for reporting SAEs are provided in Section 7.10.9.

7.10.9 **Reporting of Serious Adverse Events and Pregnancies**

7.10.9.1 Contact person(s) and number(s)

SAEs and pregnancies must be reported immediately (i.e., not later than 24 hours after first knowledge). The SAE or pregnancy report should be e-mailed or faxed to United BioSource Corporation (UBC) using the following e-mail or fax-number:

Email: [contact] [contact]

7.10.9.2 **Reporting procedures**

Serious adverse events

For each SAE, the investigator will complete a Serious Adverse Event Report Form and assess the relationship of each SAE to trial treatment. The completed form(s) should be sent immediately (and not later than within 24 hours of first knowledge of the SAE) electronically to the UBC using the SAE Reporting by email or fax.

Follow-up reports regarding the status of the SAE and the subject's subsequent course should be submitted until the SAE has subsided, the condition stabilised (in the case of persistent impairment), the subject receives alternative therapy, or the subject dies. The form and fax confirmation will be retained. Contacts for reporting SAEs, pregnancies and other safety concerns are provided to each site.

7.11 Unscheduled Visit

An unscheduled visit may be performed at any time during the trial if judged necessary by the investigator, such as for a severe reaction, suspected pregnancy, clinically significant AE, or clinically significant local skin reaction result. Details of the event are to be recorded in the subject's records.

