2.1 Study Design

This is a prospective, investigational, investigator-blind, vehicle and active-controlled, parallel-group, 3arm, randomized, phase-III trial conducted at approximately 34 sites in the European Union. The trial population consists of subjects fulfilling all inclusion and no exclusion criteria as defined in the CTP, Sections 5.2 and 5.3 with any exceptions documented [1]. Random allocation to one of three parallel treatment groups in a 3:1:3 ratio (MC2-01 cream; MC2-01 vehicle; active comparator) is stratified by site.

A total of 476 subjects are planned to be enrolled, randomized and observed until final evaluation and completion. Subjects prematurely terminating the trial will not be replaced.

The maximum trial duration for each subject will be approximately 14 weeks and includes a screening period of up to 30 days (if washout of prohibited medications is required), an 8-week treatment period, and a follow-up period of 2 weeks.

A total of seven visits and a telephone interview of subjects are planned. The telephone interview is planned for Week 2 (Visit 3), while the visits will be held at screening (Visit 0, Day -30 to 0), randomization (Visit 1, Week 0, Day 0), Visits 2, 4, and 5 at Weeks 1, 4 and 6, respectively, planned for Days 7, 28, and 42 plus/minus 2 days, respectively, Visit 6 as end of treatment Visit (Week 8, Day 56+/-2, or at early termination), and Visit 7 as follow-up visit (Week 10, Day 70+/-2). The follow-up visit is planned as an on-site visit in case of abnormal laboratory values or unresolved adverse events (AE). Otherwise, the follow-up visit is a telephone interview. At any time during the trial, if judged necessary by the investigator, unscheduled visits may be performed. For a visit schedule, see CTP Section 7.0 [1].

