At all on-site visits (Screening, Week 0, Week 1, Week 4, Week 6, Week 8, and Early Termination), the investigator will assess the extent and severity of the subjects' psoriasis on the body (trunk and/or limbs) using an mPASI scoring system for each of the 3 areas (arms, trunk, and legs). The extent (E) is scored 0 to 6. The severity of the psoriatic lesions in each of the 3 areas will be recorded for each of the signs of redness (R), thickness (T), and scaliness (S). For each clinical sign, a single score, reflecting the average severity of all psoriatic lesions on given body region, will be determined. Redness, thickness and scaliness scores are ranging from 0 to 4. The meaning of scores is summarized in the following table.

Extent (E) Redness (R) Thickness (T) Scaliness (S) Score 0 no involvement none (no erythema) none (no plaque none (no scaling) elevation) <10% mild (slight, barely 1 mild (faint erythema, mild (sparse, finepink to very light red) scale lesions, only perceptible elevation) partially covered) 2 10% to 29% moderate (definite moderate (definite moderate (coarser light red erythema) elevation but not scales, most of thick) lesions covered) 3 30% to 49% severe (dark red severe (definite severe (entire lesion elevation, thick covered with coarse erythema) plaque with sharp scales) edge) 4 50% to 69% very severe (very very severe (very very severe (very dark red erythema) thick plaque with thick coarse scales, possibly fissured) sharp edge) 5 70% to 89% 6 90% to 100%

Table 1: Overview of the meaning of mPASI scores assessed for arms, trunk and legs

Per area, the scores for extent, redness, thickness and scaliness are combined to $A = E \cdot (R+T+S)$. Ranging from a minimum score of 0 and a maximum score of 64.8, the mPASI is calculated from the scores of the extent and severity of the disease by use of the following equation:

 $mPASI = 0.2 \cdot A_{arms} + 0.3 \cdot A_{trunk} + 0.4 \cdot A_{legs}.$

At any post-baseline visit, mPASI 75 is defined as an indicator of a reduction in mPASI from baseline of 75% or more.

PGA and PGA Success on the Body and on the Scalp

PGA measures the investigator's impression of the disease at a single point using a defined, 5-point, static PGA scale (0 = clear, 1 = almost clear, 2 = mild, 3 = moderate or 4 = severe) at Screening, Weeks 0, 1, 4, 6, 8, and Early Termination.

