4.6.2 Analysis Visit Windowing

Post-baseline visits are to be held at Weeks 1, 2, 4, 6, 8 and 10, namely at study Day 7, 14, 28, 42, 56 and 70, within two days from target day. In addition, unscheduled visits and visits of Early Termination may be given. Comprehensive non-overlapping visit windows are defined for Week 4 from Day 14 to Day 42 and for Week 8 as Day 43 or later, respectively, excluding any follow-up visits.

Primary and secondary efficacy endpoints will be summarized and analysed by *analysis visits*. For Week 4 and Week 8, analysis visits are defined as the visits held closest to the target day per analysis visit window as defined above. Any other visits within the same visit window will not be considered for analysis of primary or secondary efficacy endpoints. If the time distances of two visits from the target day are identical, the later visit is selected for analysis.

Other efficacy endpoints and safety endpoints will be summarized and analysed by nominal visits as appropriate.

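### SAP 4.6.2 picks the Week 8 analysis visit by date alone, so an event-driven unscheduled visit can displace a recorded Visit 6 value

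*Protocol*

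**What the plan says.** The rule is in SAP 4.6.2. After listing the planned visits it adds: "In addition, unscheduled visits and visits of Early Termination may be given". It sets the window "for Week 8 as Day 43 or later, respectively, excluding any follow-up visits", with no upper limit. Within the window, "analysis visits are defined as the visits held closest to the target day per analysis visit window as defined above". Ties go forward in time: "If the time distances of two visits from the target day are identical, the later visit is selected for analysis". The remainder is discarded: "Any other visits within the same visit window will not be considered for analysis of primary or secondary efficacy endpoints". The section has no condition that the endpoint was measured at the selected visit, and no preference for the scheduled one.

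SAP 2.1 describes "Visit 6 as end of treatment Visit (Week 8, Day 56+/-2, or at early termination") and mentions unscheduled visits separately from the Visit 7 follow-up. Protocol 7.11 explains why unscheduled visits happen: "An unscheduled visit may be performed at any time during the trial if judged necessary by the investigator, such as for a severe reaction". The other examples there are suspected pregnancy, a clinically significant adverse event and a clinically significant local skin reaction. That section asks only for the event to be documented, and Table 7-1 has no column for such visits.

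The documents do not settle whether mPASI is scored at an unscheduled visit. SAP 2.4.1 lists the scoring visits without them ("At all on-site visits (Screening, Week 0, Week 1, Week 4, Week 6, Week 8, and Early Termination"), whereas Protocol 7.8.2 calls for scoring at every on-site visit.

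**The concern.** The rule can set aside a measured primary outcome because the subject came in for a reaction or adverse event close to Day 56. There are two cases.

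- **No score at the unscheduled visit.** The selected visit is empty and the Visit 6 value is barred from analysis. SAP 4.7.2 would then treat Week 8 as missing and impute it. The tipping-point analysis in SAP 5.5.1 could penalise that imputed value. The non-responder analysis of PGA success could turn an observed success into a failure. PTCS would fall back on an earlier score, and the subject would drop out of the per-protocol mPASI analysis, which uses no imputation.
- **A score at the unscheduled visit.** A score taken because something happened replaces the planned end-of-treatment assessment.

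In both cases the trigger may be related to treatment and outcome. The affected endpoints are percentage change in mPASI, PGA success and PTCS at Week 8, so the primary non-inferiority comparison is included. Setting aside a recorded value also conflicts with the treatment-policy strategy in SAP 5.3, under which all available data are used.

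**Working it through.** **The plan's own figure, for context.** Protocol 8.2 states 88.9% power with 204 per active arm, SD 38, margin 12, true difference 0 and two-sided alpha 0.05. The standard error is 38 × √(2/204) = 3.763, and 12/3.763 − 1.960 = 1.229, which gives 89.05% by the normal approximation. The noncentral t gives 88.91%. The stated figure is reproduced. The point does not depend on it.

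**Selection rule.** Let Visit 6 fall on day d and one unscheduled visit on day u, with u at least 43. The unscheduled visit is selected if |u − 56| < |d − 56|, or if the distances are equal and u > d. Days in the second and third columns count Visit 1 as Day 0. The last column gives days elapsed since Visit 1 when SAP 4.4.1 is applied, which adds 1 to derive the study day.

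| Visit 6 (days after Visit 1) | Displaced by an earlier unscheduled visit | Displaced by a later unscheduled visit | With the plus-1 study day (elapsed days) |
|---|---|---|---|
| 54 | none | 55–58 | later: 55–56 |
| 55 | none | 56–57 | none |
| 56 | none | none | earlier: 55 |
| 57 | 56 | none | earlier: 54–56 |
| 58 | 55–57 | none | earlier: 53–57 |

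The second column holds however the follow-up exclusion is read. The third column holds only if that exclusion does not reach an unscheduled visit after Visit 6. SAP 4.4.2 assumes treatment ends the day before Visit 6, so every visit in the third column would be off treatment. A visit exactly 56 days after Visit 1 cannot be displaced by a visit on another day when Visit 1 is Day 0. Under the plus-1 derivation it can.

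The per-protocol window in SAP 4.2.3 runs from Day 49 to Day 66. A Visit 6 on Day 66 is displaced by an earlier unscheduled visit on any of Days 47–65. A Visit 6 on Day 49 is displaced by one on Days 50–63, again only if visits after Visit 6 are eligible.

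**Size.** The documents give no rate of unscheduled visits, so the loss fraction f is an assumption. If displaced values added no information at all, n per arm becomes 204 × (1 − f):

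| f | Power (normal approximation) |
|---|---|
| 0 | 89.05% |
| 1% | 88.8% |
| 2% | 88.4% |
| 5% | 87.5% |
| 10% | 85.7% |

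This covers lost precision only. For bias, the estimated difference moves by f × δ if a fraction f of one arm has its values shifted by δ on average. Taking f = 2% and δ as large as one SD gives 0.02 × 38 = 0.76 points, against a margin of 12. Both inputs are illustrative.

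**With the fix.** If the recorded Visit 6 value has priority, no day displaces it. Planned N and power do not change.

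**The case against.** The best defence is that the SAP should be read as a whole. SAP 5.3 promises to use all available data, SAP 4.7.2 calls data missing only when unavailable, and SAP 5.7 leaves technical detail to programming specifications that are not part of these documents. A sensible programmer would not let an empty visit overwrite a recorded score. That is fair as a prediction, and the documents nowhere direct that an observed value be replaced by a blank. But SAP 4.6.2 states expressly that other visits in the window are not considered, so avoiding the problem means an undocumented departure from that sentence, for the primary endpoint.

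Second, where mPASI is scored at the unscheduled visit, a score nearer Day 56 from a blinded investigator is valid treatment-policy data, and the selection rule is the same in every arm. This stands: the issue there is replacement of the planned assessment, not inadmissible data.

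Third, a reader might infer that off-treatment visits generally displace Visit 6. The documents do not establish this. SAP 4.4.1 runs the follow-up period from Visit 6 to Visit 7, so a visit after Visit 6 may well be a follow-up visit and excluded. On that reading the third column of the table disappears and the tie rule protects Visit 6, because Visit 6 is the later visit. SAP 2.1 names unscheduled visits apart from Visit 7, so the wording is not conclusive either way.

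Fourth, a reader might extend the point to the Week 2 telephone contact, since the Week 4 window opens on Day 14. That does not threaten a primary or secondary endpoint directly. All Week 4 endpoints are in the SAP's other category, and SAP 4.6.2 analyses other efficacy endpoints by nominal visit.

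**Conclusion.** The gap is real and lies in SAP 4.6.2. Protocol 7.11 contains no error; it only shows that event-driven visits can occur. Taken literally, the windowing rule can discard a recorded Visit 6 value when Visit 6 falls on Day 57 or 58 and an unscheduled visit falls one to three days before it. For Visit 6 on Day 54 or 55 the same can follow from a later visit, but only if the follow-up exclusion does not cover visits after Visit 6. The day counts assume Visit 1 is Day 0; the plus-1 derivation shifts them.

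A reader might conclude that the non-inferiority result is materially at risk. The documents do not support that. They give no frequency, the qualifying days are few when Visit 6 is on schedule, and the power loss under an assumed 1–2% is less than one percentage point. The reason to act is that the rule leaves open which value counts as the primary outcome, and the ambiguity arises in subjects with reactions or adverse events.

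**What to change.** In SAP 4.6.2, before unblinding:

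1. Select the analysis visit separately for each endpoint, only among visits in the window at which that endpoint was recorded.
2. Use the scheduled Visit 6 or Early Termination value whenever it falls in the window. Use an unscheduled visit only if no scheduled value exists.
3. State that the excluded follow-up visits include any visit after Visit 6.

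In the same edit, say whether the windows count Visit 1 as Day 0 or use the plus-1 study day of SAP 4.4.1, and reconcile Protocol 7.8.2 with SAP 2.4.1 on whether mPASI is scored at unscheduled visits.

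The cost is a few sentences in the SAP and one condition in the visit-windowing program. Sample size, visits and data collection are unaffected.

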7.12 Follow-up Visit

An on-site follow-up visit is required for the following reasons:

- Unresolved treatment-related AEs.
- If the albumin-corrected serum calcium was above the normal reference range at the Week 8 visit a repeat test should be done 14 days (± 2 days) after.

A telephone call will be made 2 weeks after the Week 8 visit as follow-up for all subjects without unresolved treatment-related AEs or abnormal, elevated albumin-corrected serum calcium to ask for the wellbeing of the subject.

7.13 Early Termination

The subjects are free to withdraw at any time if they choose without providing reasons. All efforts will be made, however, to encourage the subject to continue in the trial or at least come for the Week 8 visit. This also is applicable in case administration of the IP has been terminated.

If the subject is considered non-compliant with protocol procedures, for example started prohibited medication, all efforts will be made to encourage the subject to continue on treatment (if no safety concerns) or at least come for the Week 8 visit.

The following procedures should be performed at the early termination visit:

- Collect all trial materials from the subject.
- Assess compliance
- Review any concomitant medication used since the previous trial visit.
- Record any AEs.
- Physical examination and vital signs
- Perform a urine pregnancy test for females of childbearing potential.
- Biochemistry and urinalysis.
- PGA
- mPASI
- BSA
- SGA
- DLQI
- EQ-5D
- Psoriasis Treatment Convenience Scale
- Local Skin Reactions

8.0 STATISTICAL METHODS AND DETERMINATION OF SAMPLE SIZE STATISTICAL AND ANALYTICAL PLANS

8.1 General Considerations for Data Analysis

The methodology presented below represents a brief overview of the statistical methods that will be fully detailed in the statistical analysis plan (SAP). The SAP will be finalised before the database is locked. Any changes to the methods described in the final SAP will be described and justified in the clinical trial report. All statistical analyses will be performed using SAS® statistical software (Version 9.2 or higher). Statistical significance will be tested at the 2-sided 5% level unless otherwise specified.

Subjects will be randomised in a 3:1:3 ratio (MC2-01 cream: MC2-01 cream vehicle: active comparator), stratifying by trial site. The aim is to randomise 14 subjects or more at each site. Furthermore, on a country level, it will be ensured that up to 30 % of the population can be subjects with mild disease (based on the PGA performed at Baseline), as monitored by data management. It is planned that the data from trial sites that participate in this trial will be combined so that an adequate number of subjects will be available for analysis. Trial sites yielding fewer than 14 subjects overall will be combined in order of geographical proximity. The exact composition of these "analysis sites" will be determined and documented prior to breaking the trial blind. In statistical models, site will refer to trial site or analysis site, if combination of trial sites is needed.

8.2 Sample Size and Power Considerations

The primary endpoint is percentage change from baseline in mPASI at Week 8. The primary endpoint will be used for superiority evaluations of MC2-01 cream and active comparator versus vehicle, and the non-inferiority evaluation of MC2-01 cream versus active comparator. The primary endpoint has been chosen as percentage change from baseline instead of absolute change, as this was the endpoint in the studies used to determine the non-inferiority margin.

The sample size calculation is based on the non-inferiority margin for the treatment difference in percentage change from baseline in mPASI at Week 8.

Non-inferiority margin:

According to information from experienced dermatologists as well as data from an observational study (28, 29), the two marketed products, Daivobet[®] Gel and Daivobet[®] Ointment, appear to be equally effective. The summary of mean reductions in mPASI in randomized trials with Daivobet[®] Gel and Daivobet[®] Ointment is shown below (Table 8-1 and Table 8-2).

Table 8-1 Published mean reduction of PASI for active treatment from baseline to 8-weeks reported in CAL/BDP Gel phase 2/3 trials

Reference	Patients N	mPASI Baseline (mean)	PASI mean reduction from Baseline to Week 8 (%)	SD
Menter 2013 (30)	482	7.9	-55.8	34.4
Langley 2011(31)	183	9.39	-57.0	29.6
Fleming 2010 (12)	162	7.7	-55.3	33.3

Table 8-2 Published mean reduction of PASI for active treatment from baseline to 8-weeks reported in CAL/BDP Ointment phase 3 trials

Reference	Patients N	mPASI Baseline (mean)	PASI mean reduction from Baseline to Week 8 (%)	95% CI	95% CI
Guenther 2002 (32)	150	9.9	-68.6	-64.8	-72.4
Kaufmann 2002 (13)	490	9.9	-71.3	-69.1	-73.6
Kragballe 2004; (33)	645	10.4	-68.7	-66.9	-70.5
Kragballe 2006 (34)					
Ortonne 2004 (35)	249	9.7	-65.0	-61.4	-68.6

CI: Confidence interval

Based on these trials, a random-effects meta-analysis of mean reduction in mPASI at end of trials shows an estimated difference of 12.71 percentage points [95% CI 8.00 to 17.41] between Daivobet[®] Gel and Daivobet[®] Ointment, suggesting that -12 percentage points is a clinically acceptable margin for non-inferiority. Therefore, the non-inferiority limit is set to -12 percentage points.

Assumptions for sample size calculation:

- The common standard deviation is assumed to be 38 (based on the assumption of an SD of 35 in the active treatment arms (see above Daivobet[®] Gel studies), 50 in the vehicle arm (found to be the largest SD in the above Daivobet[®] Gel studies), and the 3:1:3 ratio)
- The error probability is set to 0.05 for a 2-sided test

Under these assumptions, a sample size of N=204 per active treatment group for the non-inferiority evaluation, assuming 0 difference, results in a power of 88.9%. Thus, a total of 476 subjects should be randomised in a 3:1:3 ratio (MC2-01 cream: MC2-01 cream vehicle: active comparator).

MC2-01-C7

With 476 subjects randomised 3:1:3, and the assumption that the effect of both active treatments is -56 percentage points (the average effect found in the gel studies), and the effect of MC2-01 cream vehicle is -27 percentage points (the largest effect found for the ointment, found in the MCB-9905 INT study), the power for each of the superiority comparisons of MC2-01 cream and active comparator to MC2-01 cream vehicle with respect to mPASI is more than 99%. If 30% of subjects treated with either MC2-01 cream or active comparator respectively 11% of subjects treated with MC2-01 cream vehicle will have PGA success, the power for the each of the superiority comparisons with respect to PGA success is 90.4%.

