8.6.1.1 Analysis of primary endpoint

Superiority analysis

First the percentage change in mPASI from baseline to Week 8 for MC2-01 cream and the active comparator will be compared with that of MC2-01 cream vehicle for a superiority evaluation using the treatment-policy estimand for the ITT population and imputing missing data using MI.

The comparison will be done using an ANCOVA model including treatment, site, and baseline PGA as factors, and baseline mPASI as covariate. The estimated differences between MC2-01 cream and MC2-01 cream vehicle, and between active comparator and MC2-01 cream vehicle, will be reported together with the associated standard error, the 95% confidence interval, and a test corresponding to no difference between treatments.

Non-inferiority analysis

Next, if and only if superiority to MC2-01 cream vehicle can be claimed for both MC2-01 cream and active comparator on the 5% significance level, MC2-01 cream will be compared to active comparator for a non-inferiority evaluation using the treatment-regimen estimand for the ITT population and imputing missing data using MI.

Percentage change in mPASI from baseline to Week 8 will be compared between MC2-01 cream and active comparator for a non-inferiority evaluation using the -12 percentage points non-inferiority margin. The comparison will be done using the same model as applied for the analysis of superiority vs. vehicle as described above: an ANCOVA model including treatment, site, and baseline PGA as factors, and baseline mPASI as covariate. The estimated difference between MC2-01 cream and active comparator will be reported together with the associated standard error, and the 95% confidence interval. If the lower limit of the 95% confidence interval is above -12 percentage points, non-inferiority is demonstrated.

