5.4.2 Continuous Data

Continuous data will be described by summary tables of sample characteristics by visit and for changes between visits as defined in Section 3.2.2 above. Selected continuous variables will be visualized by box plots by treatment group and visit.

ANCOVA

Comparisons will be done using an ANCOVA model including treatment, analysis site and baseline PGA as factors, and the baseline value of the respective endpoint as covariate.

The statistical model is

endpoint = $\beta_0 + \beta_1$ ·baseline value + treatment + analysis site + baseline PGA + error,

where β_1 is a parameter of fixed effect and β_0 an intercept. The estimated differences between MC2-01 cream MC2-01 cream vehicle, and between active comparator and MC2-01 cream vehicle, will be reported together with the associated standard error, the 95% confidence interval, and a p-value of a test on the respective contrast corresponding to the hypothesis as either no difference between treatments (superiority) or difference between treatments within the tolerance limits (non-inferiority) (cp. Section 5.2 above).

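### The primary ANCOVA has one error variance although the plan assumes SD 35 in the active arms and 50 in the small vehicle arm: vehicle intervals come out too narrow and the non-inferiority interval too wide

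*Protocol*

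**What the plan says.** Protocol 8.2 plans with two different SDs for percentage change in mPASI: 35 in each active arm and "50 in the vehicle arm (found to be the largest SD in the above" gel studies. It merges them by the allocation ratio: "The common standard deviation is assumed to be 38 (based on the assumption of an SD of 35 in the active treatment arms". That single value is used even for the non-inferiority comparison, in which vehicle takes no part: "a sample size of N=204 per active treatment group for the non-inferiority evaluation, assuming 0 difference, results in a power of 88.9"%.

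The analysis has the same structure. SAP 5.4.2 says: "Comparisons will be done using an ANCOVA model including treatment, analysis site and baseline PGA as factors", with the baseline value as covariate. It writes the model with one undifferentiated error term and tests each hypothesis as a contrast from it. For non-inferiority, Protocol 8.6.1.1 says: "The comparison will be done using the same model as applied for the analysis of superiority vs. vehicle".

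Neither document mentions arm-specific variances, robust standard errors or a Welch-type test. The three sensitivity analyses in SAP 5.5.1 (tipping point, hypothetical strategy, per-protocol set) do not address unequal variance. Imputation is done within treatment group (Protocol 8.5, SAP 4.7.2), but each completed dataset is analysed with this same ANCOVA before pooling.

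**The concern.** An ordinary ANCOVA estimates one residual variance over all arms. With 408 of 476 subjects in the active arms, that estimate lies close to the active-arm variance. It is too small for a contrast that involves vehicle and somewhat too large for one that does not. Vehicle is the arm with both the fewest subjects and the largest assumed SD, which is the unfavourable combination.

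Two things are at stake. First, the vehicle comparisons are steps 1 and 2 of SAP Table 4, and every later confirmatory test depends on them. Step 2, comparator over vehicle, is also the trial's internal check of assay sensitivity. SAP 5.3 relies on the hierarchy to control the familywise error, which requires each step to be a valid 5% test. The vehicle differences are also to be reported with standard errors and 95% intervals, whose coverage matters whatever the p-value. Second, the non-inferiority test, which serves the primary objective, carries variance from an arm outside the comparison.

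**Working it through.** **Inputs (Protocol 8.2).** SD 35 / 50 / 35 for MC2-01 cream, vehicle and comparator. Total 476 at 3:1:3, so n = 204 / 68 / 204. Margin 12. Two-sided error 0.05. Assumed effects −56 (active) and −27 (vehicle), a difference of 29.

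**The plan's own figures.**
- Common SD: √((3·35² + 50² + 3·35²)/7) = 37.51, rounded up to 38.
- Non-inferiority SE: 38·√(2/204) = 3.76.
- Power at zero difference: Φ(12/3.76 − 1.96) = 89.05%. The noncentral t with 406 df gives 88.91%, which matches the stated 88.9%.
- Power against vehicle with SD 38 is 99.98%, consistent with the stated value above 99%.

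The sample-size arithmetic is therefore sound. The issue is what the model does with these SDs.

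**Active versus vehicle.**
- Model SE: 37.51·√(1/204 + 1/68) = 5.25.
- True SE: √(35²/204 + 50²/68) = 6.54.
- Ratio: 0.803, so the model SE is about 20% too small.
- Coverage of the nominal 95% interval: 2Φ(1.96·0.803) − 1 = 88.5%.
- Two-sided error at equal means: about 11.5%.
- 95% half-width: 10.3 as modelled, 12.8 if correct.

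**MC2-01 cream versus comparator.**
- Model SE: 37.51·√(2/204) = 3.71.
- True SE: 35·√(2/204) = 3.47.
- Ratio: 1.072, so the interval is about 7% too wide (half-width 7.28 against 6.79).
- One-sided error: 1 − Φ(1.96·1.072) = 1.8% instead of 2.5%.
- Power with the pooled variance: Φ((12 − 7.28)/3.47) = 91.3%.
- Power with the active-arm variance: Φ(12/3.47 − 1.96) = 93.4%.

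**Simulation of the three-arm ANCOVA.** 20,000 trials per scenario, 34 sites of 14 split 6:2:6, with site, baseline PGA and baseline value in the model, and complete data. Vehicle coverage was 88.4–88.5% and two-sided error 11.5%. Non-inferiority coverage was 96.1–96.4%, one-sided error 2.0% and power 91.1%.

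**Range over the vehicle SD, active SD held at 35.**

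| Vehicle SD | Vehicle CI coverage | Two-sided error | Non-inferiority CI coverage | Power vs vehicle, correct SE |
|---|---|---|---|---|
| 35 | 95.0% | 5.0% | 95.0% | >99.9% |
| 40 | 92.9% | 7.1% | 95.5% | 99.96% |
| 45 | 90.7% | 9.3% | 96.0% | 99.8% |
| 50 | 88.5% | 11.5% | 96.4% | 99.3% |

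**Power after the change, with Satterthwaite df.** For the vehicle contrast, df = (35²/204 + 50²/68)² / [(35²/204)²/203 + (50²/68)²/67] ≈ 90, so the critical value is 1.987. Power at a difference of 29 is 99.2%, still above 99%.

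**The case against.** Several points on the other side are fair.

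- **The SD of 50 is an upper-end planning value.** The protocol calls it the largest found. Table 8-1 lists only active-arm SDs (29.6 to 34.4), so 50 cannot be checked from the documents. This stands, and it is why the range is shown. The problem disappears only if the SDs are equal, which the plan does not assume.
- **The 11.5% needs a particular null:** equal means but SD 35 against 50. If MC2-01 cream behaved like vehicle in SD as well (50/50/35), the pooled SD is √((3·50² + 50² + 3·35²)/7) = 44.2. The ratio of model to true SE is then 44.2/50 = 0.884, and the step 1 error is about 8.3%. With 50 in all arms it is 5.0%. This stands as a limit on the type I error figure. The coverage shortfall does not depend on the null.
- **Few decisions change.** At a true difference of 29, the pooled test rejects with probability Φ((29 − 10.3)/6.54) = 99.8% and the correct one with Φ(29/6.54 − 1.96) = 99.3%. The two disagree in about 0.5% of trials per comparison. Non-inferiority also opens only if both vehicle tests reject, so the chance of falsely passing both cannot exceed the single-test rate. This stands.
- **The non-inferiority side is conservative,** and its 91.3% power exceeds the stated 88.9%. This also stands. The loss is relative to an analysis that uses the variance of the two arms being compared.
- **The figures are simplified.** They use raw SDs and complete data, whereas the analysis uses residual variance and multiple imputation by arm. Covariate adjustment may reduce all residual SDs, but it is the ratio between arms that drives the effect. Imputation was not simulated, so decimals should not be over-read.

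Finally, equal variance is inferred from the single error term and the planned common SD; the documents do not use the words. It is the ordinary meaning of an ANCOVA written this way.

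**Conclusion.** The concern holds. With SDs of 35/50/35 and 204/68/204 subjects, the vehicle standard errors are about 20% too small. Their nominal 95% intervals cover about 88.5%, and the type I error is about 11.5% at equal means with those SDs. The non-inferiority standard error is about 7% too large, at a cost of about two percentage points of power. The vehicle-contrast error shrinks to 9.3% and 7.1% at vehicle SDs of 45 and 40.

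This is a calibration fault in the primary model and does not threaten the likely conclusion. Superiority over vehicle would very probably be shown under either analysis, and the non-inferiority test errs on the safe side. It should still be corrected, because the plan states a 5% level and 95% intervals that its own assumptions do not deliver, and no planned sensitivity analysis would reveal it.

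**What to change.** In SAP 5.4.2, keep the ANCOVA terms as they are but allow a separate residual variance per treatment group. One way is PROC MIXED with REPEATED / GROUP=treatment and Satterthwaite or Kenward-Roger degrees of freedom. Fit it in each of the 100 imputed datasets and pool by Rubin's rule. Apply it to all mPASI percentage-change contrasts: vehicle superiority, non-inferiority, the later superiority test against comparator, Week 4 and the sensitivity analyses.

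Because this refines the model stated in Protocol 8.6.1.1, add an entry to SAP 5.6, and specify it before unblinding so that the choice is not data-driven.

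The cost is one model option and two short text changes, with no extra subjects or data. Under the plan's SDs the vehicle half-width grows from about 10.3 to 12.8 points with power still above 99%. The non-inferiority half-width falls from about 7.3 to 6.8, and its power rises from 91.3% to 93.4%.
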